### 7.3.2. Reference-based imputation

The datasets created through the code in Table 2 are then used for the reference-based imputation. The code for the reference-based imputation is as follows:

---

**Table 3. SAS code for reference-based imputation**

---

```
proc sort data= OUT_IMP_CONT;
  by _IMPUTATION_ USUBJID;
run;

proc mi data=OUT_IMP_CONT nimpute=1 round=0.1 seed=
out=CONT_BASED_CONTROL;
  by _IMPUTATION_;
  class CONMED;
  var  BASE_NRS CONMED
      DELT_NRS1 DELT_NRS2 DELT_NRS3 DELT_NRS4
      DELT_NRS5 DELT_NRS6 DELT_NRS7
      DELT_NRS8 DELT_NRS9 DELT_NRS10
      DELT_NRS11 DELT_NRS12;

  mnar modelDELT_NRS1 DELT_NRS2 DELT_NRS3 DELT_NRS4
      DELT_NRS5 DELT_NRS6 NRS7
      DELT_NRS8 DELT_NRS8 DELT_NRS10
      DELT_NRS11 DELT_NRS12;
  / modelobs=(TRT = "PBO");
run;
```

---

After the reference-based imputation is completed, the primary results are obtained, by first computing the outcome in each of the 100 imputed datasets and then combining the results across these datasets. The code for these analyses can be found below.

**Table 4. SAS code for MMRM analysis as part of the imputation process**

---

```

proc mixed data=COMBINE method=reml alpha=0.025 covtest;
  by _IMPUTATION_;
  class AVISITN(ref=LAST) TRT USUBJID CONMED;
  model DELT_NRS = BASE_NRS CONMED TRT AVISITN TRT*AVISITN
    BASE_NRS*AVISITN/ solution ddfm=kr;
  repeated VISITNUM / subject=USUBJID type=TBD r;
  estimate 'RIN - PBO AT WK 12' TRT 1 -1
    TRT*AVISITN 0 0 0 0 1 0 0 0 0 -1
    / CL;
  lsmeans TRT*AVISITN/diff;
  ods output estimates=SI_ESTIMATES;
run;

```

---

The analysis outlined in Table 4 will produce 100 estimates of the difference between the ricolinostat and placebo groups in change from baseline in NRS at Week 12. These values are contained in SI\_ESTIMATES. Note that the “type =” option in the repeated statement will need to be modified to include the covariance structure that is selected for the primary model. The output from the estimate statement should be compared to that of the lsmeans statement to ensure that the correct comparison is selected. Table 5 provides the code for the implementation of Rubin’s rules to obtain the combined estimates of treatment effect at the two dose levels.

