### **7.2. Identification of the primary model**

The primary endpoint is change from baseline in mean average pain intensity over the 12 weeks of treatment as measured by the weekly average NRS in the FAS population. The primary endpoint will be analyzed using a MMRM analysis. The MMRM will be fit with the weekly mean change from baseline in the NRS score at Weeks 1, 2, 4, 8 and 12 as the outcome. The following covariates will be included in the model: baseline NRS score, visit, treatment group, concomitant medication for painful DPN (yes vs. no), treatment group by visit interaction term, and baseline NRS score by visit interaction. A restricted maximum likelihood will be used as the method of estimation with the degrees of freedom approximated using the

Kenward Rogers approach (see Table 4 for an example of the MMRM code to be used for the primary model). The model will be fit with an unstructured covariance matrix. If the MMRM with an unstructured covariance matrix does not converge, the following covariance structures will be substituted in the order listed below. Each subsequent covariance structure will be used only if each previous covariance structure fails to converge. The covariance structure for the final model will be the first structure in the sequence that produces a stable model that converges.

1. Toeplitz covariance structure (assuming measurements taken closer together in time are more highly correlated than those taken farther apart).
2. First order auto-regressive (AR[1]) covariance structure (assuming measurements taken closer together in time are more highly correlated than those taken farther apart, but more constrained than the Toeplitz structure).
3. Compound symmetry covariance structure (assuming equal correlation for measurements from a patient, regardless of how far apart in time when they were taken).

Once the primary model is established, this model will be used for all analyses.

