**Table 2. SAS code to create datasets satisfying monotone missing condition**

---

```

** Rearrange data for use in PROC MI;
proc sort data= DATA_IMP(observed data set);
    by USUBJID TRT BASE_NRS;
run;

proc transpose data= DATA_IMP out=DATA_IMP1;
    by USUBJID TRT BASE_NRS;
    ID AVISITN;
    VAR DELT_NRS;
run;

proc sort data= DATA_IMP1;
    by USUBJID;
run;

proc mi data=DATA_IMP1 nimpute=100 round=0.1 seed=
out=OUT_IMP_TRT_RIN;
    where TRT eq "RIN";
    var    BASE_NRS(baseline) CONMED
           DELT_NRS1 DELT_NRS2 DELT_NRS3 DELT_NRS4
           DELT_NRS5 DELT_NRS6 DELT_NRS7 DELT_NRS8
           DELT_NRS9 DELT_NRS10 DELT_NRS11 DELT_NRS12;
    mcmc  chain=multiple impute=monotone;
run;

proc mi data=DATA_IMP1 nimpute=100 round=0.1 seed=
out=OUT_IMP_TRT_PBO;
    where TRT eq "PBO";
    var    BASE_NRS(baseline) CONMED
           DELT_NRS1 DELT_NRS2 DELT_NRS3 DELT_NRS4
           DELT_NRS5 DELT_NRS6 DELT_NRS7 DELT_NRS8
           DELT_NRS9 DELT_NRS10 DELT_NRS11 DELT_NRS12;
    mcmc  chain=multiple impute=monotone;
run;

data OUT_IMP_CONT;
    set OUT_IMP_TRT_RIN OUT_IMP_TRT_PBO;
run;

```

---

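### The example ESTIMATE statement for the primary Week 12 difference (SAP Table 4) does not code the contrast in its label: under the SAP's own CLASS order it is non-estimable

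*SAP*

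**What the plan says.** SAP 7.2 fits the primary MMRM to the weekly mean change in "NRS score at Weeks 1, 2, 4, 8 and 12 as the outcome" and points to Table 4 as an example of the code. In Table 4:

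- The classification statement is "class AVISITN(ref=LAST) TRT USUBJID CONMED". Visit comes before treatment, and no reference level or order option is set for TRT.
- The treatment contrast begins "estimate 'RIN - PBO AT WK 12' TRT 1 -1" and continues with "TRT*AVISITN 0 0 0 0 1 0 0 0 0 -1". There are no coefficients for AVISITN itself.
- The output of that statement is stored in SI_ESTIMATES. The text after the table says the analysis "will produce 100 estimates of the difference between the ricolinostat and placebo groups in change from baseline in NRS at Week 12".
- The same text adds a check: "The output from the estimate statement should be compared to that of the lsmeans statement", so that the right comparison is picked.

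The treatment codes are RIN and PBO in Table 2, and RIC and PBO in Tables 6 and 7. SAP 7.3.1 says of the code presented there that it is not final and will be vetted on blinded data. Table 5 applies Rubin's rules to a dataset called LSM, by TRT and VISITNUM. It does not read SI_ESTIMATES.

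**The concern.** A positional ESTIMATE statement gives the intended contrast only if its coefficients follow the order in which the software lays out the parameter columns. Here the ten interaction coefficients are written as if all five visits of one arm came first, then all five of the other. The CLASS statement produces the opposite nesting. The label also presumes that the active arm is the first treatment level, but PBO sorts before both RIN and RIC.

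The SAP names this statement as the source of the 100 differences behind the primary result, and the sensitivity analyses in SAP 7.4 reuse Table 4. Direction matters too: a lower NRS is better, and the tipping-point steps in SAP 7.4 begin from whether the test favours ricolinostat.

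**Working it through.** **Inputs.** Five visits (SAP 7.2); two arms coded PBO and RIN (SAP Table 2); CLASS order AVISITN, then TRT (Table 4); the printed coefficients (Table 4). Two assumptions come from SAS defaults and not from the documents: interaction columns follow CLASS order with the later variable changing fastest, and levels are sorted by value, so PBO precedes RIN.

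**Step 1: count the cells.** 2 arms × 5 visits = 10, which matches the ten printed coefficients. The statement was evidently written for the five-visit model.

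**Step 2: place the coefficients.** With AVISITN first, the columns run as follows:

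| Position | 1 | 2 | 3 | 4 | 5 | 6 | 7 | 8 | 9 | 10 |
|---|---|---|---|---|---|---|---|---|---|---|
| Week | 1 | 1 | 2 | 2 | 4 | 4 | 8 | 8 | 12 | 12 |
| Arm | PBO | RIN | PBO | RIN | PBO | RIN | PBO | RIN | PBO | RIN |
| Coefficient | 0 | 0 | 0 | 0 | +1 | 0 | 0 | 0 | 0 | -1 |

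The +1 falls on placebo at Week 4 and the -1 on ricolinostat at Week 12.

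**Step 3: test estimability by hand.** In this over-parameterised model, each observation in arm t at visit v contributes 1 to the TRT column for t, 1 to the AVISITN column for v and 1 to their interaction column. In any estimable contrast, the coefficient on each visit must therefore equal the sum of that visit's interaction coefficients over arms.

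- Required by the printed interaction: Week 4 = +1 + 0 = +1; Week 12 = 0 + (-1) = -1.
- Supplied: 0 for both.

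The condition fails, so the contrast is non-estimable. Supplying the missing visit terms would make it estimable, but it would then compare placebo at Week 4 with ricolinostat at Week 12.

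**Step 4: test numerically.** I built the Table 4 fixed-effects design (intercept, baseline, CONMED, TRT, AVISITN, TRT by AVISITN, baseline by AVISITN) and checked whether L(X'X)⁻(X'X) = L. Where the contrast was estimable, I fitted simulated data with a true RIN minus PBO of -0.8 at Week 12. Neither estimability nor sign depends on the covariance structure.

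| CLASS order | Arm sorted first | Position 5 / position 10 | Result |
|---|---|---|---|
| AVISITN, TRT (as printed) | PBO (default) | PBO Wk 4 / RIN Wk 12 | non-estimable, max deviation 0.333 |
| AVISITN, TRT | RIN (forced) | RIN Wk 4 / PBO Wk 12 | non-estimable, max deviation 0.333 |
| TRT, AVISITN | PBO (default) | PBO Wk 12 / RIN Wk 12 | estimable, +0.83 |
| TRT, AVISITN | RIN (forced) | RIN Wk 12 / PBO Wk 12 | estimable, -0.85 |

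Each estimable row was fitted to its own simulated dataset, so the values differ from ±0.8 by sampling error. Without noise, the third row gives +0.8.

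The labelled contrast appears only in the fourth row, which needs both a reordered CLASS statement and the active arm forced first. If the columns followed the effect as written (TRT then AVISITN) instead of CLASS order, the third row would apply.

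**Step 5: effect of a sign reversal on the test.** Replacing L by -L changes t to -t and leaves |t|, and so the two-sided p-value, unchanged.

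**Step 6: check a corrected statement.** Keep the printed CLASS order with PBO first, and use `TRT -1 1` with `TRT*AVISITN 0 0 0 0 0 0 0 0 -1 1`. The visit sums are then 0 at every week (Week 12: -1 + 1 = 0), which matches the absence of visit coefficients. The contrast is estimable and gave -0.73 in one simulated dataset with a true value of -0.8, so its sign agrees with the label.

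**The case against.** The strongest reply is that this is draft code whose failure cannot pass unnoticed. SAP 7.2 calls Table 4 an example, and its covariance type is still a placeholder. SAP 7.3.1 promises vetting, although that sentence introduces the imputation code. A non-estimable contrast yields no number. The step may stop even earlier, because REPEATED names VISITNUM, which is not in CLASS. The LSMEANS comparison would then show the discrepancy. All of this stands and limits the severity, but none of it corrects the statement.

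A reader might infer more than the documents support:

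- **That the primary result will carry the wrong sign, an error of 0.8 - (-0.8) = 1.6 points.** The reversal needs a CLASS order that the SAP does not use. As printed, Table 5 also pools LSM and not SI_ESTIMATES, so the documents do not show the mislabelled value reaching the report.
- **That no arrangement gives the labelled difference.** One does: treatment first in CLASS, with the active arm ordered first.
- **That the model might run on 12 visits.** The statement is non-estimable there too, and Tables 2 and 3 do impute all 12 weeks. But SAP 7.2 fixes five visits, and the step that builds the long analysis dataset is simply not printed.
- **That the LSMEANS check cannot reveal direction.** Under the same level order its difference would also be placebo minus ricolinostat, so the numbers would agree. But its output names the arms, and a careful reader would see the conflict with the label.

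What remains is a narrower risk. The obvious repair for non-estimability is to swap the CLASS order, and that alone produces a plausible number under the wrong label. Blinded or randomly assigned treatment codes would give no known direction to set it against.

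**Conclusion.** The ESTIMATE statement in Table 4 is wrong as written. Under default SAS ordering with five visits it is non-estimable, so SI_ESTIMATES would contain no usable Week 12 difference. If only the CLASS order is swapped, it returns placebo minus ricolinostat under the reverse label, with an unchanged two-sided p-value. The estimand, the model and the hypothesis test in SAP 7 and 7.2 are not affected.

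I rate this a minor-to-moderate correction to pre-specified code. It rests on the two SAS defaults listed above and on no format or order option being applied to TRT elsewhere. The ±0.8 figures illustrate direction, using the design difference from SAP 6.1.1; they do not predict an error in the reported effect.

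**What to change.** 1. Replace the positional statement with a non-positional Week 12 contrast: LSMESTIMATE, or the Week 12 LSMEANS difference with placebo set as reference. If a positional statement is kept with the current CLASS order and PBO first, use the coefficients verified in Step 6.
2. Write that row to the dataset that PROC MIANALYZE reads, and change Table 5 to match.
3. Use one active-arm code in all the code tables, and one visit variable in CLASS, REPEATED and Table 5.
4. State in SAP 7 that the difference is ricolinostat minus placebo and that a negative value favours ricolinostat.
5. Before unblinding, run the code once on simulated data with a known difference, to confirm both value and sign.

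The cost is a few lines of code and one sentence of text, with no change to the design, the data collected or the sample size.

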**Table 5. SAS code for Rubin’s rule**

---

```

proc mianalyze data=LSM alpha=0.05;
  by TRT VISITNUM;
  modeleffects estimate;
  stderr stderr;
  ods output ParameterEstimates=Week_12_MMRM_LSM;
run;

```

---

#### 7.4. Sensitivity analyses

The following sensitivity analyses will be performed:

1. MMRM based on the data as observed, noting that incomplete diary data for a given week is defined as missing (see Section 6.1.5.1). A MMRM will be fit to the data using all non-missing values. This analysis will use a modification of the code presented in Table 4.
2. A MMRM model will be fit using missing at random imputation. Using this approach all missing values will be imputed based on the treatment group to which the patient was randomized.
3. A tipping point analysis will be conducted to assess the robustness of the result and the validity of the missing at random assumption.

The code for the use of missing at random multiple imputation is provided below. The input dataset to execute this code is OUT\_IMP\_CONT which is obtained from running the code provided in Table 2. After running the code in Table 6, the code provided in Table 4 and Table 5 is executed with the dataset names changed as needed.

**Table 6. SAS code for missing at random imputation**

---

```

proc sort data= DATA_IMP_CONT;
    by USUBJID;
run;

proc mi data=OUT_IMP_CONT (where= (TRT="RIC")) nimpute=1 round=0.1
    seed= out=IMPDAT_RIC;
    by _IMPUTATION_;
    class CONMED;
    var BASE_NRS CONMED
        DELT_NRS1 DELT_NRS2 DELT_NRS3 DELT_NRS4
            DELT_NRS5 DELT_NRS6 DELT_NRS7 DELT_NRS8
            DELT_NRS9 DELT_NRS10 DELT_NRS11 DELT_NRS12;
    monotone reg (DELT_NRS1 DELT_NRS2 DELT_NRS3 DELT_NRS4
        DELT_NRS5 DELT_NRS6 DELT_NRS7 DELT_NRS8
        DELT_NRS9 DELT_NRS10 DELT_NRS11
            DELT_NRS12)/details);
run;

proc mi data=OUT_IMP_CONT (where= (TRT = "PBO")) nimpute=1
round=0.1 seed= out=IMPDAT_PBO;
    by _IMPUTATION_;
    class CONMED;
    var BASE_NRS CONMED
        DELT_NRS1 DELT_NRS2 DELT_NRS3 DELT_NRS4
            DELT_NRS5 DELT_NRS6 DELT_NRS7
            DELT_NRS8 DELT_NRS9 DELT_NRS10
            DELT_NRS11 DELT_NRS12;
    monotone reg (DELT_NRS1 DELT_NRS2 DELT_NRS3
        DELT_NRS4 DELT_NRS5 DELT_NRS6
        DELT_NRS7 DELT_NRS8 DELT_NRS9 DELT_NRS10
            DELT_NRS11 DELT_NRS12/details);
run;

data RANDOM_IMP_MAR;
    set IMPDAT_RIC IMPDAT_PBO;
run;

```

---

A tipping point analysis will be used to assess the validity of the MAR assumption.

1. The datasets generated from the code in Table 2 will be used for this analysis.
2. The PROC MI procedure in SAS is applied to each of the 100 datasets subsetted to the placebo group and all missing values in the placebo group are imputed. These 100 datasets will then be used for the tipping point analysis. These datasets can be obtained from the code for the placebo patients in Table 6.

3. For the tipping point analysis with a shift parameter, patients in the ricolinostat group with a missing value will be multiply imputed separately from the placebo-treatment arm and are assigned a shift parameter in the imputation procedure for progressively worse (higher) scores to find the point at which statistical significance is lost. Specifically, if the outcome of the hypothesis test favors ricolinostat over the placebo group (p-value <0.05), then one point is added as a shift parameter in the imputation for the ricolinostat group, while keeping the data for the placebo group unchanged. This is implemented using the code in Table 7.
4. A mixed model repeated measures (MMRM) model is used to analyze each of the 100 completed data sets. PROC MIANALYZE is used to combine these results to obtain the final estimates for the given value of the shift parameter. (See Table 4 and Table 5).
5. This “NRS shifting”, as outlined in steps 3 and 4, is repeated with one shift point at a time until the hypothesis test no longer rejects the null hypothesis in favor of the ricolinostat group over the placebo group (i.e., when the p-value becomes greater than 0.05). Additional increments may be used to locate the tipping point. If the result is not quite statistically significant, progressively higher scores are added to find the point at which statistical significance is attained. The code to generate the imputed datasets for this analysis is provided in Table 7.

All results will be summarized in tables and a forest plot.

---

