#### 4.2.1. *Numerical Pain Rating Scale (NRS)*

NRS is an 11-point assessment measure where 0 represents no pain and 10 is the worst pain possible assessed after 12 weeks. The NRS is a validated tool commonly used for pain assessment. The NRS will be recorded daily by patients.

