#### 7.3.1. *Imputation of intermittent missing values*

The imputation of the intermittent missing values is executed using the code below. Note that the code presented here is not final and will be vetted on blinded data prior to use for the final analyses. The variables to be included in the analyses are as follows:

- DELT\_NRS – change from baseline in NRS. Note that DELT\_NRSX denotes the change from baseline in NRS at Week X.
- BASE\_NRS – baseline value of NRS

- AVISITN – denotes visit number
- CONMED – a yes/no variable indicating use of concomitant pain medication
- TRT – denotes treatment group
- USUBJID – denotes patient ID

---

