**Table 7. SAS code for tipping point analysis**

---

```
proc mi data= OUT_IMP_CONT (where=(TRT="RIC")) nimpute=1 round=
  seed= out=IMPDAT_TRT;
  by _IMPUTATION_;
  var BASE_NRS CONMED
      DELT_NRS1 DELT_NRS2 DELT_NRS3 DELT_NRS4
      DELT_NRS5 DELT_NRS6 DELT_NRS7 DELT_NRS8
      DELT_NRS9 DELT_NRS10 DELT_NRS11 DELT_NRS12;

  monotone reg (/details);

  mnar adjust (DELT_NRS /shift=&S.);
run;

data COMBINE;
  set IMPDAT_TRT IMPDAT_PBO;
run;
proc sort data=COMBINE;
  by _IMPUTATION_;
run;
```

---

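### The tipping-point rule for a near-miss result (SAP 7.4, step 5) shifts imputed ricolinostat scores the wrong way, so it cannot find the point where ricolinostat becomes significant

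*SAP*

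**What the plan says.** SAP section 7.4 lists three sensitivity analyses for the primary endpoint. The third is a tipping-point analysis, set out in five steps.

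- **Step 3** covers a result that favours ricolinostat at p<0.05. Missing ricolinostat values are "assigned a shift parameter in the imputation procedure for progressively worse (higher) scores to find the point at which statistical significance is lost". One point at a time is added in the ricolinostat group, "while keeping the data for the placebo group unchanged".
- **Step 5, first part,** repeats this until the test "no longer rejects the null hypothesis in favor of the ricolinostat group over the placebo group".
- **Step 5, second part,** covers the near miss: "If the result is not quite statistically significant, progressively higher scores are added to find the point at which statistical significance is attained". It refers to the same code, in Table 7.

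Table 7 restricts the data to the ricolinostat arm and applies the shift through "mnar adjust (DELT_NRS /shift=&S", a macro variable with no stated sign or range. On the NRS, "0 represents no pain and 10 is the worst pain possible" (SAP 4.2.1), so a ricolinostat benefit is a negative ricolinostat-minus-placebo difference in change from baseline.

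Protocol section 10.3.3 also shifts only the ricolinostat arm. It seeks the point where significance changes, and it gives no direction.

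**The concern.** One upward shift of one arm cannot serve both purposes. If adding pain to the imputed ricolinostat values erodes a significant benefit, it also erodes a benefit that just missed significance.

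After a near miss, the useful question is how much better the missing ricolinostat values would have to be for the result to reach p<0.05. The rule as written cannot answer it. Testing is two-sided, and the near-miss sentence, unlike the sentence for the significant case, names no favoured arm. Read literally, the procedure could therefore run on until the difference turns significant for placebo and record that as the point where significance was attained.

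**Working it through.** **Inputs from the documents.** Two-sided alpha 0.05 (SAP 6.1.3); 274 evaluable patients, SD 2.35, difference 0.8, 80% power (SAP 6.1.1); 1:1 allocation (SAP 3.2), so 137 per arm.

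**The plan's own figure.** 0.8/2.35 = 0.34. A two-sample t-test with 137 per arm has power 0.802, so 274 is reproduced and the SD and arm size can be used below.

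**Assumptions.** The documents give no missing-data rate. The check takes a share *m* of ricolinostat values imputed, from 10% to 30%, and a near-miss difference of -0.50.

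**Formula.** With shift *s* applied to the imputed ricolinostat values only:

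- Difference: D(s) = -0.50 + m·s
- Variance: a + b·s², where a = 2 × 2.35²/137 = 0.0806 and b = m(1-m)/137
- z(s) = D(s)/√(a + b·s²)

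At s = 0 the SE is √0.0806 = 0.284, so z = -0.50/0.284 = -1.76 and p = 0.078.

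**Direction.** The sign of dz/ds is that of

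m(a + b·s²) - (-0.50 + m·s)·b·s = m·a + 0.50·b·s,

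which is positive for every s ≥ 0. So z rises with each upward step from -1.76 and moves away from the -1.96 needed for ricolinostat.

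**Results at m = 15%.**

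| Shift | Difference | z | p | Favours |
|---|---|---|---|---|
| -1 | -0.65 | -2.28 | 0.023 | ricolinostat (significant) |
| 0 | -0.50 | -1.76 | 0.078 | ricolinostat |
| +1 | -0.35 | -1.23 | 0.22 | ricolinostat |
| +2 | -0.20 | -0.69 | 0.49 | ricolinostat |
| +3 | -0.05 | -0.17 | 0.87 | ricolinostat |
| +9 | +0.85 | +2.15 | 0.031 | placebo (significant) |

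**Range over the missing share.**

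| m | First whole-point upward shift with p<0.05 | p at a shift of -1 (favours ricolinostat) |
|---|---|---|
| 10% | none up to +10 | 0.035 |
| 15% | +9, favours placebo | 0.023 |
| 20% | +6, favours placebo | 0.014 |
| 30% | +4, favours placebo | 0.005 |

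**Check with imputation uncertainty.** The formula treats all 137 values per arm as known. A simplified single-endpoint multiple imputation (100 imputations, Rubin's rules, equal missing share in both arms, 60 replicates at each of the four shares) gave no replicate out of 240 that was significant for ricolinostat at any shift from 0 to +10. The first placebo-favouring steps were none up to +10, then +9, +7 and +5. A shift of -1 gave mean p = 0.046, 0.036, 0.030 and 0.021.

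**Check on the equal-means assumption.** The formula takes imputed and observed ricolinostat means as equal before shifting. If imputed values started lower, an upward shift could shrink the variance. A grid with a starting gap of up to 10 points either way, shares of 2% to 50%, starting p of 0.051, 0.06 and 0.1, and shifts to +10 found no case of p<0.05 in favour of ricolinostat.

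**The case against.** The strongest reply concerns consequence. Step 4 already produces an estimate for each shift, and step 5 puts all results in tables and a forest plot, so a crossing on the placebo side would be visible. The preceding sentence speaks of rejection in favour of ricolinostat, and a programmer would see p rising at the first step. The placebo-side crossings also need large shifts: a weekly mean raised by 9 stays on the 0 to 10 scale only if it started at 1 or below. The figures come from a single-endpoint approximation rather than the MMRM, and the simple formula makes the -1 shift look stronger than the imputation check does.

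Most of that stands, and it limits the harm: misreporting is possible but would probably be noticed. It does not repair the rule. Noticing that p rises shows that the instruction fails; it does not supply a prespecified one.

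Three other readings were considered:

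- **Raise placebo instead.** Step 3 holds placebo unchanged, and Table 7 and the protocol shift ricolinostat only.
- **Higher means better.** Step 3 equates higher with worse.
- **The code settles it.** The macro takes whatever sign the text dictates. SAP 7.3.1 says "the code presented here is not final and will be vetted on blinded data", but vetting code does not correct a direction stated in prose.

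**Conclusion.** The direction in step 5 is wrong for its stated purpose. The point estimate rises with every upward shift whatever the missing share, so the conclusion does not depend on the assumed -0.50 or the assumed missing rates; those affect only where the placebo-favouring crossing falls. That no upward shift reaches p<0.05 for ricolinostat is algebraic when imputed and observed means start equal, and otherwise rests on the grid. The numerical checks do not use the full MMRM, and none bounds scores at 10.

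The reach is small: one branch of one of three sensitivity analyses, entered only after a non-significant result. A missed primary already stops the fixed sequence (SAP 8.2), so this branch is descriptive. The primary test, the type I error, the sample size and the tipping point for a significant result are unaffected. It should be corrected because the rule gives a wrong answer if followed.

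**What to change.** Replace the near-miss sentence in step 5 with wording such as: *When the result misses significance, progressively lower (better) scores, that is negative shifts, are applied to the imputed ricolinostat values with placebo unchanged, until p<0.05 in favour of ricolinostat. The sign and size of the shift are reported.*

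The cost is one sentence. It should be made before unblinding; the blinded data review in SAP 5.1 is a stated place to finalise methods. A later reversal would be a post hoc change to justify in the study report (SAP 1). The sign change itself needs no new code, since the macro variable accepts a negative value.

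Two separate slips in Table 7 can be settled when the code is vetted. It selects the active arm as `RIC`, whereas Table 2 builds it as `RIN`. It also adjusts `DELT_NRS`, whereas its variable list contains only `DELT_NRS1` to `DELT_NRS12`.
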